9. INVESTIGATIONAL MEDICINAL PRODUCT (IMP)

9.1. IMP Description

The principal IMP is oral sildenafil, given at 25mg TDS for one week, then automatically increased to 50mg TDS for a further 2 weeks, if tolerated, as determined by its provision in labelled dispensing packs. If side-effects occur at the higher dose, the dose will be returned to the lower dose. Sildenafil is a phosphodiesterase 5 inhibitor, widely used for erectile dysfunction and used in selected patients with primary pulmonary hypertension.

The comparator will be placebo, also taken three times daily.

The secondary comparator IMP is cilostazol, as a positive control, provided at 50mg bd and titrated to 100mg bd after one week, to continue for 2 further weeks. Cilostazol is a phosphodiesterase 3 inhibitor used at this dose in peripheral arterial disease, and used in large randomised controlled Trials of patients with previous stroke, with a beneficial effect compared to aspirin.¹⁹ It is expected to improve cerebral reactivity²² and pulsatility²⁰ and is included as a positive control to assess whether sildenafil has a similar magnitude of physiological effect, to estimate if a sufficient magnitude of clinical effect would be expected, to justify larger clinical trials. In order to preserve the blinding of this study, whilst taking cilostazol twice a day participants will be given placebo to take at midday. This means that, from the participant's perspective, they are always taking the study medication three times daily.

Participants will start sildenafil and cilostazol at lower doses for a week before being titrated up to the high dose. The high dose is similar to the medication's use in usual care, given more frequently in the case of sildenafil, but the titration is necessary to settle the participants on the new medication.

Medications will be overencapsulated, overlabelled and blinded by the Huddersfield NHS Pharmacy Manufacturing Unit, and dispensed by the Oxford University Clinical Trials pharmacy. Medications will be provided in 'dosette' type packaging providing dosing times, such that throughout the study patients will take TDS medication (sildenafil TDS, placebo TDS, cilostazol – placebo – cilostazol). Code-break will be

provided to and retained by the Oxford University Clinical Trials Pharmacy, with individual code-breaking allowed on request of the CI ([name]) when clinically indicated.

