11. STATISTICS

11.1. Description of Statistical Methods

A statistical analysis plan will be signed off prior to analysis.

Primary outcome :

Change in Gosling's Pulsatility Index from baseline to follow up, utilising the visually-assessed, better quality TCD recording (defined by blinded assessor) will be compared between sildenafil and placebo phases by paired T-test, comparing change in MCA-PI from baseline to after 3 weeks of treatment.

Secondary outcome:

The non-inferiority analysis will be based on the 95% CI for the mean change difference between sildenafil and cilostazol. If the upper 97.5% confidence limit is less than 0.08 units (2/3 of the clinically estimated overall cilostazol effect), non-inferiority will be declared.

Differences in reactivity to CO₂ from baseline in each of three states (sildenafil, cilostazol, placebo) will be compared by mixed-effect general linear models, with post-hoc pairwise comparison.

Tertiary outcomes

Equivalent statistical techniques will be used to determine responses to each of the further physiological measures for sildenafil versus placebo as the primary comparison (paired t-test for continuous outcomes), and mixed-effect linear models across the three groups. MRI imaging outcomes will be compared by analysis tools within the FSL software library, utilising linear models for interaction between drug allocation and BOLD-response to carbon dioxide. Secondly, the relevance of derived physiological indices including home blood pressure, arterial stiffness, cerebral autoregulation, peripheral vascular reactivity and beat-to-beat blood pressure variability will be determined both as predictors of cerebral pulsatility and autoregulation in linear models, and for the interaction between drug class and these indices on cerebral pulsatility and reactivity.

Individuals missing either sildenafil or placebo interventions will be excluded from the analysis corresponding to the primary objective but included in the safety analysis. Participants without cilostazol exposure will be included in the sildenafil-placebo comparison, but not in the - secondary and tertiary analyses.

Safety data will be presented for all patients who are randomised and receive at least one dose of one treatment. Safety data will be summarised descriptively.

Genetic / biochemical predictors of response to treatment will be assessed by mixed linear models for continuous outcomes, and paired t-test for binary measures.

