1.3 Trial objectives

Primary objective

To assess whether 3 weeks of treatment with sildenafil (a PDE5 inhibitor) reduces cerebral arterial pulsatility on transcranial ultrasound, compared to placebo in patients with chronic vascular injury to the brain (small vessel disease).

Secondary objectives

1. To assess whether 3 weeks of treatment with sildenafil alters cerebral arterial reactivity to carbon dioxide on transcranial ultrasound, compared to placebo (The null hypothesis is that there is no difference in the mean change between the sildenafil and placebo groups)
2. To assess whether 3 weeks of treatment with sildenafil has non-inferior effects on cerebral arterial pulsatility and reactivity to carbon dioxide on transcranial ultrasound, compared to cilostazol (The null hypothesis is that sildenafil is unacceptably inferior to cilostazol i.e. the change in mean flow velocity upon CO₂ challenge with sildenafil differs from that with cilostazol by more than the non-inferiority margin Δ).

3. To assess whether 3 weeks of treatment with sildenafil or cilostazol increases cerebral arterial reactivity to carbon dioxide on MRI, compared to placebo, in normal appearing white matter and within white matter hyperintensities.

Tertiary objectives (exploratory and mechanistic)

1. To assess whether 3 weeks of treatment with sildenafil or cilostazol increases cerebral arterial reactivity to carbon dioxide on MRI, compared to placebo, for all defined cerebral tissue type (all white matter and grey matter) and on a voxel-wise basis.
2. To assess whether there is an increased incidence of adverse events or serious adverse events with sildenafil or cilostazol compared to placebo.
3. To assess whether 3 weeks of treatment with sildenafil or cilostazol affects the following physiological parameters, compared to placebo:
 - a) Systolic and diastolic blood pressure on 1 week of home blood pressure monitoring
 - b) Arterial stiffness (carotid-femoral pulse wave velocity)
 - c) Aortic pulse pressure
 - d) Beat-to-beat and day-to-day variability in systolic blood pressure
 - e) Flow mediated slowing
 - f) Resting state cerebral autoregulation (transfer function analysis derived gain, phase and coherence between beat-to-beat blood pressure and cerebral blood flow velocity during a minimum of 5 minutes of monitoring).

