2.3 Sample size

At a power level of 0.9, with a 2-sided significance of 5%, a clinically relevant 0.12 unit change in pulsatility index (equivalent to a ~20% difference in risk of recurrent stroke), and conservatively allowing for a standard deviation of differences in PI between repeated measures of 0.2, gives an estimated minimum sample size of 32 patients (paired t-test). Allowing for a 15% drop-out rate, 38 patients would be required. A sample size of 66 achieves 90% power to detect the non-inferiority of sildenafil c.f. cilostazol using a non-inferiority margin of 0.08 (and mean of paired differences 0) at $\alpha=0.025$ (for a 95% CI) with a within-subject variance of 0.02. This equates to 75 patients in total with a 12% drop out rate.

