2.4 Statistical interim analyses, data review and stopping guidelines

The DSMB will review recruitment and safety data after 30 patients have been recruited to the study or 12 months after the first visit of the first patient (whichever is sooner) or at the request of the sponsor or CI. Data will be reviewed in a blinded form, except where significant SAEs (in the opinion of the DSMB) or a potentially important number of severe AEs have occurred, when the data will be unblinded upon the request of the DSMB. No efficacy or futility interim analysis is planned.

If after 12 months recruitment falls below the rate expected to complete the study in 3 years, allowing for delays due to the COVID-19 outbreak, the overall study size can be reduced to 50 participants. Any data collected to that date, including on cilostazol, will be retained and analysed according to the original study plan.

The proportion of total within-patient SAEs of any grade occurring until the end of the relevant wash out period or 30 days after taking the last tablet (whichever is greater) will be compared between a) sildenafil vs placebo and b) cilostazol vs placebo using McNemar's test. "Statistically significant excess" is defined as a statistically significant result at the 5% level i.e. a test with a p-value<0.05. Any statistically significant excess of SAEs in the treatment arm, or occurrence of unexpected treatment-related SAEs of sufficient severity (in the view of the DSMB), may result in early cessation of the study. The DSMB will review the total number of SAEs and AEs on a yearly basis, and the Chair of the DSMB will be informed of any SAEs that occur within 15 days of the event.

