5.1 Primary outcome

Gosling's MCA-PI will be compared between sildenafil and placebo treatment by paired t-test and a 95% confidence interval if normality distribution assumptions hold, or the non-parametric Wilcoxon signed rank test. If the placebo phase is not available, a comparison between the baseline value and sildenafil period will be accepted. The analysis will be re-run using the PP population as a sensitivity analysis, and using the percentage change at each phase from baseline.

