5.2 Secondary outcomes

The percentage change in mean blood flow velocity per mmHg during inhalation of air, 4% and 6% carbon dioxide versus medical air estimated from the beta-coefficient from a phase-shifted linear regression will be compared between sildenafil and placebo treatment by paired t-test and a 95% confidence interval if normality distribution assumptions hold, or the non-parametric Wilcoxon signed rank test. The analysis will be re-run using the PP population as a sensitivity analysis, and using the percentage change from baseline.

A non-inferiority analysis will be based on the 95% CI for the mean change difference between sildenafil and cilostazol. If the upper 97.5% confidence limit is less than 0.08 units (=inferiority margin, 2/3 of the clinically estimated overall cilostazol effect), non-inferiority will be declared. The data will be transformed if normality assumptions do not hold. The PP population will be used for this analysis, with the ITT population being used in a sensitivity analysis.

Differences in reactivity to CO₂ from baseline in each of three states (sildenafil, cilostazol, placebo) will be compared by mixed-effect general linear models, with post-hoc pairwise comparison, using the ITT population with the PP population being used in a sensitivity analysis. This will apply to both TCD measures of CO₂ reactivity and by ROI on MRI. On MRI, these analyses will also be performed on a voxel-wise basis by use of the FLAME tool (FSL).

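### Non-inferiority to cilostazol on MCA-PI is declared without any planned check that cilostazol beat placebo on MCA-PI in this trial

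*SAP*

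**What the plan says.** SAP 5.2 bases non-inferiority on the 95% CI for sildenafil minus cilostazol, with this rule: "If the upper 97.5% confidence limit is less than 0.08 units (=inferiority margin, 2/3 of the clinically estimated overall cilostazol effect". Protocol 11.1 has the same rule, again with the margin given as "2/3 of the clinically estimated overall cilostazol effect), non-inferiority will be declared". SAP 2.3 sizes this comparison "using a non-inferiority margin of 0.08 (and mean of paired differences 0", with a within-subject variance of 0.02.

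Protocol 9.1 explains why cilostazol is in the trial: it is "included as a positive control to assess whether sildenafil has a similar magnitude of physiological effect", so as to judge whether larger trials are justified.

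The comparisons with placebo are these:

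- **SAP 5.1 (primary):** MCA-PI "will be compared between sildenafil and placebo treatment by paired t-test and a 95% confidence interval". Cilostazol is not involved.
- **SAP 5.2 (mixed model):** "each of three states (sildenafil, cilostazol, placebo) will be compared by mixed-effect general linear models, with post-hoc pairwise comparison". This covers CO2 reactivity on TCD and MRI, not MCA-PI.
- **SAP 1.3 (tertiary objective 3):** "To assess whether 3 weeks of treatment with sildenafil or cilostazol affects the following physiological parameters, compared to placebo". The list has blood pressure, arterial stiffness, aortic pulse pressure, pressure variability, flow-mediated slowing, autoregulation and alternative CO2-reactivity estimates. MCA-PI is not on it.
- **Protocol 11.1 (tertiary):** three-group models for the further physiological measures, and interactions of drug class with those indices on pulsatility. Neither is a cilostazol-placebo contrast on MCA-PI.

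**The concern.** The margin is two thirds of an assumed cilostazol effect, so that effect is 0.08 / (2/3) = 0.12 units. A sildenafil-cilostazol interval below 0.08 shows that part of the effect is retained only if cilostazol has such an effect here. If it has none, the interval shows only that two ineffective treatments are alike.

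The effect cannot be taken as given. By its title in the reference list, the pulsatility trial cited for cilostazol studied acute lacunar infarction. This trial enrols patients more than one month after a lacunar or cryptogenic stroke or TIA.

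At stake is the purpose stated in protocol 9.1. A non-inferiority declaration could be taken as evidence that sildenafil matches an effective comparator when the trial has not shown that the comparator was effective. If the declaration came with a non-significant primary, the SAP gives no rule for reading the two together.

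**Working it through.** **Inputs.** From SAP 2.3 and 3.1: margin 0.08; upper limit of a two-sided 95% CI (one-sided 0.025); within-subject variance 0.02, so SD of paired differences = √(2 × 0.02) = 0.20; 66 pairs, from 75 participants less 12% (75 × 0.88 = 66). SAP 2.4 adds that "the overall study size can be reduced to 50 participants"; 50 × 0.88 = 44.

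**The plan's own figure.** n = ((1.960 + 1.282) × 0.20 / 0.08)² = 65.7, so 66, and 66 / 0.88 = 75. This agrees with the SAP. Power at 66 pairs is 90.1% by the normal formula and 89.3% by exact t.

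**Two inert drugs.** The true sildenafil-cilostazol difference is then 0, which is also the value assumed for the power calculation. The chance of a declaration is P(T > t₀.₉₇₅,ₙ₋₁), where T is noncentral t with n − 1 df and noncentrality 0.08√n / 0.20.

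| Pairs | Noncentrality | Critical t | P(declared) |
|---|---|---|---|
| 66 | 3.25 | 1.997 | 0.893 |
| 50 | 2.83 | 2.010 | 0.792 |
| 44 | 2.65 | 2.017 | 0.737 |

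For an assumed SD of differences of 0.15 or 0.25, the probability is 0.99 or 0.73 at 66 pairs, 0.96 or 0.60 at 50, and 0.93 or 0.55 at 44.

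**Joint results, both drugs inert.** These come from simulated three-period trials (at least 100,000 per setting) with independent within-subject errors of variance 0.02, paired t intervals, complete data, and no period or carryover effect.

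| Pairs | Declared, primary favours sildenafil | Declared, primary does not favour sildenafil | Declared, cilostazol superior to placebo |
|---|---|---|---|
| 66 | 0.025 | 0.87 | 0.014 |
| 50 | 0.024 | 0.77 | 0.010 |
| 44 | 0.024 | 0.71 | 0.008 |

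**Power of the missing contrast.** If cilostazol's true effect is 0.12, a paired t-test against placebo has power 0.998 at 66 pairs, 0.986 at 50 and 0.973 at 44.

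**Effect of requiring cilostazol superiority, 66 pairs.**

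| True effect, sildenafil / cilostazol | Margin met | Margin met and cilostazol superior |
|---|---|---|
| 0.12 / 0.12 | 0.89 | 0.89 |
| 0.08 / 0.08 | 0.89 | 0.79 |
| 0.06 / 0.06 | 0.89 | 0.57 |
| 0.12 / 0.04 | 1.00 | 0.36 |
| 0.12 / 0 | 1.00 | 0.03 |
| 0 / 0.05 | 0.22 | 0.06 |
| 0 / 0.06 | 0.12 | 0.04 |

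**The case against.** **The 89% is only the design power.** It is the power at a true difference of 0, and any non-inferiority rule read alone behaves this way. SAP 2.5 has the primary and secondary outcomes analysed together, so a reader would see the sildenafil-placebo result, and a misleading pair of results is rare (0.025). This stands as a partial safeguard. It does not close the gap: the declaration is not conditional on the primary, and the primary cannot show that cilostazol worked.

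**The endpoint is inferred.** The non-inferiority paragraph in SAP 5.2 does not name MCA-PI, and SAP 1.3 words the null in terms of flow velocity on CO2 challenge. For CO2 reactivity the three-state model would supply the contrast. MCA-PI is still the sound reading, because 0.08 is the pulsatility-index margin of SAP 2.3 and secondary objective 2 covers pulsatility. The passages need reconciling.

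**The 50 and 44 figures are contingencies.** They apply only if the study is reduced and all participants still receive cilostazol. Protocol 10.7 also allows the cilostazol phase to be dropped, which would leave fewer pairs. This is correct; 66 is the planned case.

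**Cilostazol superiority is too strict a condition, or not enough.** If sildenafil itself beats placebo, two inert drugs are no longer the likely explanation. A condition met when either drug beats placebo would hold inert-drug declarations to 0.034 at 66 pairs and keep the claim at 0.998 for true effects of 0.12 and 0.04. But that supports a statement that sildenafil works, which the primary already gives, not one that it retains cilostazol's effect. Conversely, superiority does not validate the assumed 0.12: if cilostazol's true effect is 0.05 or 0.06, an inert sildenafil passes both conditions in about 6% or 4% of trials. The condition is therefore necessary, not sufficient.

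**Conclusion.** The concern holds. Followed exactly, the rule gives the same answer whether both drugs work or neither does: two inert drugs would be declared non-inferior in 89% of trials at the planned 66 pairs. Requiring cilostazol to be superior to placebo on MCA-PI reduces this to 1.4%.

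The figures rest on the plan's SD of differences of 0.20, on complete pairs, and on MCA-PI being the endpoint. The per-protocol set, which is primary for this analysis, may hold fewer pairs. The primary analysis is unaffected. This is a gap in a secondary objective that should be closed before unblinding.

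**What to change.** Add to SAP 5.2:

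1. Name MCA-PI as the endpoint of the 0.08 rule, and reconcile the null hypothesis in SAP 1.3 with it.
2. Compare MCA-PI between cilostazol and placebo in the population used for non-inferiority (per protocol, with ITT as sensitivity), giving the estimate, 95% CI and two-sided 5% test. The SAP uses ITT first for its MCA-PI superiority test, so say that per protocol comes first here to match the non-inferiority set.
3. Report all three pairwise differences together.
4. State that meeting the 0.08 limit is interpreted as sildenafil retaining cilostazol's effect only if cilostazol is superior to placebo, and that this is a necessary condition.
5. If cilostazol is not superior, still report the sildenafil-cilostazol difference and CI, make no efficacy claim from non-inferiority, and rest any conclusion about sildenafil on its comparison with placebo.

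The cost is one extra contrast on data already collected, plus a less frequent retained-effect claim when cilostazol's true effect is below 0.12, as tabulated above. Where sildenafil has a 0.12 effect and cilostazol little or none, that claim is mostly withheld, but the sildenafil-placebo conclusion (power 0.998 at 66 pairs) is untouched.

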5.3 Missing data

All physiological data will be reviewed and cleaned by automated and manual processes to reduce artefactual data. The completeness and correctness of the data will be monitored as per the monitoring plan. Derived indices will be calculated from raw data by assessors blind to treatment allocation, and for primary and secondary analyses will be performed before data lock. No missing data adjustments will be used, except where a valid baseline measure is missing. In these circumstances, a baseline value will be imputed from the whole population data, using placebo arms only. Analyses will be run with and without outliers (spurious data).

5.4 Protocol pre-specified tertiary/exploratory analyses

The imaging analysis is specified in the protocol and this document. This will be completed and followed by the CI and relevant team members. Blood will be stored and then analysed at completion of the study, as the extent of testing will depend upon the demonstrated effect of medications in the study, whilst allowing for assessment of new biochemical and genetic markers reported during the study. Analysis of the markers of endothelial function and genetic targets of the trial medications (to be analysed in the two years after the last visit of the last participant) will also be detailed separately.

6. Safety data

Safety data will be routinely collected at each follow-up, including clinical history of side effects or adverse events, clinical examination and blood tests (FBC, U+Es, LFTs). The safety population will be used to summarise the adverse event data.

Adverse events (AEs) will be presented in tabular form a) per participant (see e.g. Table 6.1 below; all patients taking at least one tablet will be included) and b) per treatment administered in each period (e.g. see Table 6.2 below) including the wash-out (to a maximum of 30 days since the last tablet was taken). For each treatment within each patient, only the maximum severity of each type of AE will be displayed.

Table 6.1 Example of AE table

Adverse event (AE)		No. of participants	No. of AEs
e.g. Headache	No AE under any of the three treatments		
	No AE under sildenafil or cilostazol but AEs observed under placebo		
	No AE under sildenafil but AEs observed under placebo and cilostazol		

	AE observed under sildenafil but not under cilostazol or placebo		
	AE observed under sildenafil and cilostazol but not placebo		
	AE observed under sildenafil, cilostazol and placebo		

Table 6.2 Example of AE table

Period	Treatment	No. of participants taking treatment	No. of mild AEs	No. of moderate AEs	No. of severe AEs
First	Sildenafil				
	Cilostazol				
	Placebo				
Second	Sildenafil				
	Cilostazol				
	Placebo				
Third	Sildenafil				
	Cilostazol				
	Placebo				

SAEs are reportable for up to 30 days following the last administration of a trial drug whether after the end of a trial or between trial phases following a prolonged washout period and will be listed in full.

7. Statistical software

All analysis will be carried out using appropriate validated statistical software such as STATA, SAS or R. The relevant package and version number will be recorded in the final report.

8. References

3. Julious SA. Sample sizes for clinical trials with normal data. *Stat Med.* 2004;23(12):1921-1986
4. CONSORT 2010 statement: extension to randomised crossover trials *BMJ* 2019;366:l4378
<https://www.bmjjournals.org/lookup/doi/10.1136/bmjjournals.125405>

https://www.ema.europa.eu/en/documents/scientific-guideline/ich-e-9-statistical-principles-clinical-trials-step-5_en.pdf

9. Document history

Version	Date	Comments/justification	Protocol version	Timing in relation to unblinding of trial statistician
0.1	07Mar2021	First draft	3.0	Prior to unblinding
0.2	19Jan2022	Second Draft	3.0	Prior to unblinding
0.3	25/06/2022	First approved version	3.0	Prior to unblinding
0.4	31/01/2023	Revision of Approved version	3.0	Prior to unblinding
0.5	27/02/2023	Revision of Approved version	3.0	Prior to unblinding

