 - g) Alternative estimates of CVR (change in mean flow velocity per unit change in etCO₂) determined during hyperventilation, 4% CO₂ and 6% CO₂, each versus air.

2. Trial design

OxHARP is a randomised, placebo and actively controlled, three-arm double-blind (patient and clinician), assessor-blinded crossover trial. Using random allocation, participants will have three weeks of treatment with each of the following: sildenafil (25mg TDS, titrated to 50mg TDS after one week), placebo (one tablet TDS, titrated to 2 tablets after one week), cilostazol (50mg BD, titrated to 100mg BD after one week, with midday placebo). Following each treatment period, participants will undergo a clinical and physiological assessment, followed by at least one week washout before starting the next treatment. A subgroup of participants will undergo MRI imaging following sildenafil and placebo treatments to assess arterial pulsatility on MRI and cerebrovascular reactivity, and a further subgroup will undergo MRI on all three treatments. The primary objective will be assessed using a superiority hypothesis testing framework and a non-inferiority framework will be used for the secondary objective.

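### SAP Table 6.1, the example per-participant adverse-event table, lists six of the eight treatment patterns, so cilostazol cannot be compared with placebo or sildenafil from it

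*SAP*

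**What the plan says.** Tertiary objective 2 in SAP section 1.3 covers both active drugs: "To assess whether there is an increased incidence of adverse events or serious adverse events with sildenafil or cilostazol compared to placebo". The trial is a three-treatment crossover; under SAP section 2, "participants will have three weeks of treatment with each of the following".

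SAP section 6 (Safety data) describes its first AE display in these words: "presented in tabular form a) per participant (see e.g. Table 6.1 below; all patients taking at least one tablet will be included". A second display goes by treatment within each period, for which Table 6.2 is the model. The first shell is titled "Table 6.1 Example of AE table" and uses headache as its sample event. It has columns for number of participants and number of AEs, and six rows:

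- "No AE under any of the three treatments"
- "No AE under sildenafil or cilostazol but AEs observed under placebo"
- events on placebo and cilostazol, none on sildenafil
- "AE observed under sildenafil but not under cilostazol or placebo"
- events on sildenafil and cilostazol, none on placebo
- events on all three

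Table 6.2 gives each treatment a row in each period, with the number of participants treated and counts of mild, moderate and severe AEs. It has no column for event type. SAEs are listed in full (SAP section 6), and SAP section 2.4 compares SAEs on each active drug with placebo by McNemar's test. Protocol section 11.1 says that safety data are summarised descriptively.

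**The concern.** A table that classifies people by response pattern is useful only if every person falls in exactly one row. Here two patterns have nowhere to go, and they are not evenly placed. Both matter for any comparison involving cilostazol, and neither matters for sildenafil against placebo.

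Table 6.1 is the only planned display that shows, for a named event, how many participants had it on one treatment and not on another. That within-person view is what a crossover adds to safety reporting. Copied as printed, the shell would serve the sildenafil half of tertiary objective 2 and not the cilostazol half.

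A second gap concerns exposure. The table takes in everyone who had a single tablet, yet each row describes an outcome under all three treatments. The text does not say where to place someone who never took one of them.

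**Working it through.** **Step 1: enumerate the patterns.** Three treatments, each with AE yes or no, give 2³ = 8 patterns. Write S, C, P for sildenafil, cilostazol and placebo, with 1 = event and 0 = none.

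| S C P | Row in Table 6.1? | S vs P | C vs P | S vs C |
|---|---|---|---|---|
| 0 0 0 | yes | same | same | same |
| 0 0 1 | yes | differ | differ | same |
| 0 1 0 | **no** | same | differ | differ |
| 0 1 1 | yes | differ | same | differ |
| 1 0 0 | yes | differ | same | differ |
| 1 0 1 | **no** | same | differ | differ |
| 1 1 0 | yes | differ | differ | same |
| 1 1 1 | yes | same | same | same |

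Each paired comparison has four discordant patterns. Sildenafil versus placebo keeps four of four. Cilostazol versus placebo and sildenafil versus cilostazol each keep two of four. This step needs no assumption.

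**Step 2: illustrate the size.** The documents give no AE rates, so the rates s, c, p below are assumptions. N = 75 is the planned total (SAP section 2.3). Under independence within person:

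- cilostazol only = (1−s)·c·(1−p)
- sildenafil plus placebo = s·(1−c)·p

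At s/c/p = 30/30/10%:

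- cilostazol only = 0.7 × 0.3 × 0.9 = 0.189, or 14.2 of 75
- sildenafil plus placebo = 0.3 × 0.7 × 0.1 = 0.021, or 1.6 of 75
- no row: 0.189 + 0.021 = 0.210, or about 16 of 75
- cilostazol rate recovered from the rows: 0.300 − 0.189 = 11.1%
- sildenafil rate recovered: 0.300 − 0.021 = 27.9%

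The same sums at other assumed rates give the next table. 'C not P' means an event on cilostazol and not on placebo; 'P not C' is the converse.

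| s/c/p | No row, of 75 | C not P: true, shown | P not C: true, shown |
|---|---|---|---|
| 10/10/5% | 6.8 | 9.5%, 1.0% | 4.5%, 4.1% |
| 20/20/10% | 12.0 | 18.0%, 3.6% | 8.0%, 6.4% |
| 30/30/10% | 15.8 | 27.0%, 8.1% | 7.0%, 4.9% |
| 40/40/20% | 18.0 | 32.0%, 12.8% | 12.0%, 7.2% |
| 50/50/20% | 18.8 | 40.0%, 20.0% | 10.0%, 5.0% |

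The first two lines reverse direction; the other three do not. The fraction of C-not-P participants lost is 1 − s, so it is half when s = 50% and more at lower sildenafil rates.

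At 30/30/10% the two active drugs have equal rates, and each truly has 21% of participants with an event on it but not on the other. The rows show 18.9% for sildenafil but not cilostazol, and 2.1% for cilostazol but not sildenafil.

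**Step 3: allow for correlation within person.** With a shared latent liability of correlation 0.5 at 30/30/10%, 14.3% of participants still have no row (0.143 × 75 = 10.7), and the sildenafil–cilostazol contrast reads 12.6% against 1.7%. Over the five rate sets, reversal of C versus P survives only at 10/10/5% when the correlation is 0.3, and in none of them when it is 0.5.

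**Step 4: exposure.** The sample size allows 12% drop-out, which is 0.12 × 75 = 9 participants, and Protocol section 10.7 lets the cilostazol phase be removed if recruitment is very slow. Participants who miss at least one treatment are therefore foreseeable.

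**The case against.** **It is only an example.** The table is titled as one, cited with 'e.g.' and filled with a sample event. The commitment is to a per-participant table, not to these six rows. This stands: the harm arises only if the shell is used literally. But a printed shell is what a programmer copies.

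**The gap would show.** Under the five rate sets and independence, the rows would add to about 56 to 68 of 75, so a careful statistician would notice. This also stands, although the shortfall could not be divided between the two missing patterns from the table itself.

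**Cilostazol events are reported elsewhere.** Table 6.2 counts them by period and severity with its own denominators, SAEs are listed in full, and SAEs on cilostazol are tested against placebo. A reader might infer that the trial report would present cilostazol as safer than it is; the documents do not support that. What remains is narrower: Table 6.2 has no event-type column and McNemar's test covers SAEs only, so neither replaces the paired view by event.

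**A row may have been lost in reading the PDF.** The table breaks after the third row, where a cilostazol-only row would naturally sit, so this cannot be excluded. One row lost there would not also explain the missing sildenafil-plus-placebo row, which belongs in the lower block. If only that row were missing, the loss would fall on placebo-not-cilostazol participants and would count against cilostazol. The sponsor can settle this from the source file.

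**Unexposed participants.** A reader might infer that people who never took a drug are to be coded as event-free on it. The SAP says only "all patients taking at least one tablet will be included". The coding is unspecified, not stated wrongly.

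**Conclusion.** Wrong as written, but minor and presentational. The shell omits two of eight patterns, and that rests on counting alone. Used as laid out, it preserves sildenafil versus placebo and cannot support cilostazol versus placebo or sildenafil versus cilostazol for any event type. In that table, cilostazol can look safer than it is.

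The size rests on assumed AE rates and an assumed within-person correlation. At 30/30/10% under independence, 21% of participants are unclassified; positive correlation shrinks the loss without removing it. The stronger claim, that the table would reverse the cilostazol–placebo direction, holds only at low assumed rates with little correlation and should not be made in general.

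No hypothesis test, estimate or decision rule in the SAP depends on this table.

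**What to change.** In SAP section 6, add two rows to Table 6.1: one for an event on cilostazol alone, and one for an event on sildenafil and placebo with none on cilostazol. With these, the eight rows account for everyone who took all three treatments.

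Add a sentence limiting the eight-row classification to those participants. Show people who took only one or two treatments in separate rows, or with treatment-specific denominators, so that non-exposure is not read as absence of an event. Before editing, check the source file for a row at the page break.

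The cost is an edit to a table shell, with no new data and no additional analysis. The SAP's document history records earlier revisions made before unblinding, so there is a precedent for such a change.
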